4.1. Treatment Design

Memory – as cognition in general – is based on synchronous oscillatory activity within and across neuronal networks. Neuronal network activity can be modified via non-invasive brain stimulation. Transcranial alternating current stimulation (tACS) is a well-established and safe form of non-invasive stimulation. Stimulation frequency and location is chosen to engage the neuronal networks of interest as a function of the psychological constructs investigated in a given study. Here, we will use gamma-frequency-tuned tACS targeting bilateral temporal lobes during cognitive testing including a verbal memory task, with ultra-delayed recall on the day after the stimulation and after five days.

There is evidence for the improvement of episodic memory through the use of tACS in the gamma-frequency range in healthy participants ((8), (9), (10), (11)). We favor the temporal lobes over other locations for stimulation because gamma band brain activity occurs in temporal neocortex and hippocampus, both during memory encoding in the awake state and during memory consolidation in slow wave sleep ((12), (13), (14)).

We decided for an alternative frequency (21 Hz) as control intervention in order to match the side effects associated with bilateral temporal stimulation. The tACS amplitude will be titrated individually (evaluation of side effects; start with 2mA peak-to-peak, -0.25mA until side effects tolerable for at least 1 hour, respective testing for 40 Hz and for 21 Hz, lower well-tolerated amplitude is being administered during tasks).

4.2. Experimental Design

This is a controlled cross-over study. Participants will be randomly allocated to the respective sequence (first tACS, then control stimulation – vice versa) via simple randomization, i.e. based on a single sequence of random sequence numbers generated by computer.

4.3. Measurement Design

Table 1. Variables of interest: their occasions of evaluation, their uses for the aims, their roles in the study

| Variables within Domains | Scale ¹ | Occasions ² | Aims ³ | Main Roles |
|---|---------------------|------------------------|-------------------|---------------------------|
| Identifiers | | | | |
| Participant's unique ID | Nominal | All | All | Identifier |
| Intervention (A or B)* | Binary | E | All | Identifier |
| General Profile | | | | |
| Age | Decimal yrs | S | All | Screening, covariate uses |
| Implanted device/hearing aid | Binary | S | All | Screening |
| Cardiac pacemaker | Binary | S | All | Screening |
| Willingness to abstain from alcohol ≥24h before visit | Binary | S | All | Screening |
| Known neurologic diseases | Binary | S | All | Screening |
| Known psychiatric diseases | Binary | S | All | Screening |
| Known other medical conditions | Binary | S | All | Screening |
| Brain surgery in the past | Binary | S | All | Screening |
| Night shifts, bed after midnight | Binary | S | All | Screening |
| Use of illegal drugs | Binary | S | All | Screening |
| Sex | Categorical | 0 | All | Covariate uses |
| Racial/ethnic categories | Categorical | 0 | All | Covariate uses |
| Education | Categorical | 0 | All | Covariate uses |
| Living conditions | Categorical | 0 | All | Covariate uses |
| Work status | Categorical | 0 | All | Covariate uses |
| Clubs/social organizations | Binary | 0 | All | Covariate uses |
| Sports | Binary, categorical | 0 | All | Covariate uses |
| Social contacts | Binary, categorical | 0 | All | Covariate uses |
| Media consumption | Categorical | 0 | All | Covariate uses |
| Concomitant medications list | Nominal | 0 | All | Covariate uses |

| | | | | |
|--|---|----------------------------|--------------|--|
| Caffeine consumption | Binary, nominal, dL | 0 | All | Covariate uses |
| Alcohol consumption | Binary, nominal, dL | 0 | All | Covariate uses |
| Smoker | Binary, yrs, cig/d | 0 | All | Covariate uses |
| Questionnaires | | | | |
| Sleep Quality Assessment PSQI (15) | Ordinal 0-21 | 0 | All | Screening |
| Patient Health Questionnaire-9 (16) | Ordinal 0-27 | 0 | All | Screening |
| General Anxiety Disorder-7 (17) | Ordinal 0-21 | 0 | All | Screening |
| Alcohol Use Disorders Identification Test (1-3) (18) | Ordinal 0-18 | S | All | Screening |
| AD8 Dementia Screening (19) | Ordinal 0-8 | 0 | All | Screening |
| Montreal Cognitive Assessment (20) | Ordinal 0-30 | 0 | All | Screening |
| Epilepsy Screening (21) | Binary | 0 | All | Screening |
| Handedness Questionnaire (22) | Laterality Index | 0 | All | Covariate uses |
| Behavioral Inhibition and Behavioral Activation Self Report Scales (BIS/BAS) (23) | Ordinal, 4 subscales: BIS (7 to 28) BAS drive (4-16) BAS fun-seeking (4-16) BAS reward (7-20) | 0 | All | Covariate uses |
| Basic Sleep Habits | hh:mm; hours/min | 0 | All | Covariate uses |
| Stimulation conditions | | | | |
| Epileptiform activity in EEG | Binary | 0 | All | Early termination of study participation |
| Karolinska Sleepiness Scale (24) | Ordinal 1-10 | D1A, D2A, D1B, D2B | Aim 2 | Covariate use |
| PANAS (Positive and Negative Affect Schedule) (25) | Ordinal 20-100 | D1A, D2A, D1B, D2B | Aim 2 | Covariate use |
| Sleep quality night before | Categorical (nominal) | D1A, D2A, D1B, D2B | Aim 2 | Covariate use |
| Cognitive testing | | | | |
| Completed | Binary | D1A, D2A, D1B, D2B | Aim 1 | Primary outcome |
| Delayed and ultra-delayed recall from Rey Auditory Verbal Learning Test (RAVLT) (26) and from word | Ratio (number of correct words); number of correct words for trials 1-5 (=learning), for trial 6 ("interference") and for trial 7 ("recall"); | D1A, D2A, PA, D1B, D2B, PB | Aim 2, Aim 5 | Primary outcome |

| | | | | |
|---|---|----------------------------|-------|---|
| association test; RAVLT encoding | number of confabulations and perseverations in total) | | | |
| Time from encoding of RAVLT and word association test to delayed and ultra-delayed recall | Interval (hh:mm) | D1A, D2A, PA, D1B, D2B, BP | Aim 2 | Covariate use |
| Time from encoding of word association test to delayed and ultra-delayed recall | Interval (hh:mm) | D1A, D2A, PA, D1B, D2B, BP | Aim 2 | Covariate use |
| RAVLT | Ratio (number of correct words for trials 1-5 (=learning), for trial 6 ("interference") and for trial 7 ("recall"); number of confabulations and perseverations in total) | D1A, D1B | Aim 2 | Covariate use |
| Word association test | Ratio (number of correct words for trials 1-4) | D1A, D1B | Aim 2 | Covariate use |
| Letter Fluency (28) | Ratio (number of correct words, number of perseverations and number of rule breaks) | D1A, D2A, D1B, D2B | Aim 6 | Secondary outcome |
| Stroop Color and Word Test (29) | Interval (sec), ratio (errors) | D1A, D2A, D1B, D2B | Aim 6 | Secondary outcome |
| Trail Making Test A and B (30) | Interval (sec), ratio (errors) | D1A, D2A, D1B, D2B | Aim 6 | Secondary outcome |
| Test of Attentional Performance (TAP) (31) | Interval, ratio (Alertness: Percentile rank of median reaction time for correct responses, percentile rank of standard deviation; Go/NoGo: Percentile rank of median reaction time for correct responses, percentile rank of standard deviation, percentile rank of errors; Divided Attention: Percentile rank of median reaction time for correct responses, percentile rank of standard deviation, percentile rank of errors, percentile rank of omissions; Visual Scanning: Percentile rank of median of critical and non-critical, respective standard deviation, omissions) | D1A, D2A, D1B, D2B | Aim 6 | Secondary outcome |
| Sleep EEG | | | | |
| First night with ≥4 hours of recording | Binary (hh:mm) | N1 | Aim 3 | Primary outcome; early termination of study participation if <4 hours |
| EEG worn for ≥4h hours in 3/3 nights | Binary (nights) | N1, N2A, N2B | Aim 3 | Primary outcome |

| | | | | |
|---|-------------------------------------|--------------------|--------------|---------------------|
| Sleep latency | Minutes | N1, N2A, N2B | Aim 4, Aim 5 | Covariate use |
| Sleep efficiency | % | N1, N2A, N2B | Aim 4, Aim 5 | Covariate use |
| Sleep spindles, slow wave sleep | Amount/hour | N1, N2A, N2B | Aim 4, Aim 5 | Primary outcome |
| Subjective tolerability of headband | Binary, nominal | N1, N2A, N2B | Aim 3 | Exploratory use |
| Actigraphy | | | | |
| Motor activity/24 hours, resting time for sleep | %, hours | N2A, D2A, N2B, D2B | Aim 7 | Exploratory outcome |
| Thresholding | | | | |
| TMS motor threshold | % MSO (maximal stimulator output) | D2A | Aim 8 | Exploratory outcome |
| tACS thresholding | mA (lower value of 21 Hz and 40 Hz) | D2A | Aim 8 | Exploratory outcome |
| Safety Monitoring | | | | |
| AEs and SAEs documentation | Events | All | All | Safety monitoring |

¹ Units of measurement or the scale.

² Occasions of evaluation or retrieval:

S = Screening

0 = Enrollment and Baseline

N1 = Night 1

D1A = Day 1 in Intervention A

N2A = Night 2 in Intervention A

D2A = Day 2 in Intervention A

PA = Phonecall in Intervention A

D1B = Day 1 in Intervention B

N2B = Night 2 in Intervention B

D2B = Day 2 in Intervention B

PB = Phonecall in Intervention B

³ The specific aims in which the variable will play a role in data analyses.

⁴ Uses: assess medication adherence, mediation analyses, and exploratory analyses

*Intervention:

A = tACS

B = control stimulation

5. Study Participants

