During stimulation, the participants will perform the following cognitive tests presented on the computer screen or on paper: RAVLT (Rey Auditory Verbal Learning Test) (26), a word association test (8 word-pairs), Letter Fluency (28), Stroop Color and Word Test (29), Trail Making Test A and B (30), TAP (Test of Attentional Performance) (31). The stimulator will be triggered by remote control from the experiment script and will administer stimulation during each single test. After each block of stimulation, an eyes-open resting state EEG will be performed. All stimulation involves 20 seconds of ramp-in time and 20 seconds of ramp-out time. The total duration of the stimulation and testing is approximately 40 minutes.

7. Schedule of Activities and Procedures

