8.1. Strategies that Apply to all the Aims

All testing described below assumes a significance threshold of $p = 0.05$. Analyses will be deemed to be statistically significant if the p-value is less than this threshold. An analysis that does not exceed this threshold will be considered inconclusive. The proposed statistical analysis strategy acknowledges that no p-value can reveal the plausibility, presence, truth, or importance of an association or effect.

There may be additional covariates included in the analysis. Data will be assessed for normality and, if deemed necessary, corrective procedures will be applied (e.g., log normalization). This correction will be applied upon consideration of the variables themselves, and not based on the result of the intended analysis.

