8.3 Aim-Specific Plans

Plans for Aim 1.

a) The proportion of participants in which stimulation and cognitive testing could be completed will be calculated after both stimulation sessions, i.e. visit 2 and visit 4 (percentage and 95% confidence interval).

Plans for Aim 2.

To evaluate the effect of gamma-tACS on cognitive testing.

a) Primary outcome: Ultra-delayed verbal memory recall (i.e. amount of words and word associations remembered the day after encoding the RAVLT) after gamma-tACS compared to after control stimulation, intra- and interindividually.

We will perform a two-way or one-way repeated measure ANCOVA with time (baseline and post-treatment) and treatment (control vs gamma-tACS) as within-subjects factors, and the order in which tACS will be applied (tACS-sham or control tACS) as covariate. Post-hoc tests will be calculated after Bonferroni correction for multiple comparisons.

Null hypothesis: There is no difference between tACS and control stimulation for ultra-delayed memory recall one day after stimulation. Alternative hypothesis: Memory recall is better after gamma-tACS than after control stimulation.

b) Secondary outcomes: Verbal and associative learning (immediate and delayed recall, recall after 5 days) and executive functions (results of Letter Fluency, Stroop Test, Trail Making Test, Tests of Attentional Performance), comparison intra- and interindividually, after gamma-tACS and control stimulation (comparison of difference

between visit 1-visit 2 and visit 3-visit 4; comparison of absolute results of visit 1 versus visit 3 and visit 2 versus visit 4; statistical tests and covariates as in a)).

Hypotheses are the same as for the primary outcome.

Plans for Aim 3.

To investigate the feasibility and adherence to wearable device (single-channel EEG during the night).

a) The proportion (percentage and 95% confidence interval) of participants with at least four hours of EEG recording in the first night.

b) The proportion (percentage and 95% confidence interval) of participants with at least four hours of recorded nocturnal data for each of all three nights.

Plans for Aim 4.

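### Table 1 lists learning scores taken under stimulation and next-day ratings as Aim 2 covariates; if they enter the recall model, it no longer estimates the total effect in section 8.3

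*Combined protocol and SAP*

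**What the plan says.** Table 1 in section 4.3 assigns each variable its occasions, its aims and its main role. Four kinds of entry matter here.

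- **Word-pair learning:** "Word association test | Ratio (number of correct words for trials 1-4) | D1A, D1B | Aim 2 | Covariate use".
- **RAVLT learning, interference and recall trials (1-5, 6, 7):** the row ends "number of confabulations and perseverations in total) | D1A, D1B | Aim 2 | Covariate use".
- **Ratings:** "Karolinska Sleepiness Scale (24) | Ordinal 1-10 | D1A, D2A, D1B, D2B | Aim 2 | Covariate use" and "Sleep quality night before | Categorical (nominal) | D1A, D2A, D1B, D2B | Aim 2 | Covariate use". The PANAS mood row has the same occasions and role.
- **Primary-outcome row:** its label, which covers delayed and ultra-delayed recall, also includes "association test; RAVLT encoding".

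Footnote 3 to the table explains that the Aims column shows the aims in whose data analyses a variable will be used.

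D1A and D1B are the stimulation days. Section 6 says that the stimulator "will administer stimulation during each single test", and section 7.4 places both the RAVLT and the word association test in the stimulated block at Visits 2 and 5. D2A and D2B are the following days.

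Section 8.3 gives the Aim 2 hypothesis as better next-day recall after gamma-tACS than after control. Its ANCOVA names one covariate, the order of the two conditions. It also lists as a secondary outcome "Verbal and associative learning (immediate and delayed recall, recall after 5 days"). Section 8.1 adds: "There may be additional covariates included in the analysis". It names none.

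**The concern.** The hypothesis in section 8.3 concerns the total effect of stimulation on recall, by whatever route. Section 4.1 motivates the stimulation site by gamma activity at two stages: encoding while awake and consolidation in slow wave sleep. A learning score taken with the current on lies on the first route. A rating of the night after stimulation, or of sleepiness and mood the next day, may lie on the second.

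A covariate affected by treatment and related to the outcome takes part of the treatment effect with it. What remains is the effect not passing through that variable, which is a different quantity from the one hypothesised. The contrast at stake is next-day recall, which section 8.3 and Table 1 both call primary. The choice would also be open after the data are seen, because Table 1 offers these covariates and section 8.3 does not rule them out.

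**Working it through.** **1. Timing of each candidate covariate (Table 1 and section 7.4)**

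| Variable | Occasion | Relative to that period's stimulation |
|---|---|---|
| Sleepiness, mood, sleep quality | D1A, D1B | Before (Visit 2 step 2 precedes step 5; Visit 5 step 3 precedes step 4) |
| RAVLT trials 1-7, word-pair trials 1-4 | D1A, D1B | During |
| Sleepiness, mood, sleep quality | D2A, D2B | After; sleep quality here describes the night following stimulation |

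The last two rows are post-treatment. The first is not.

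**2. The plan's own figure.** Section 5.1.2 gives n = 28 for dz = 0.5, power 0.80 and alpha 0.05, without stating sidedness. By the noncentral t distribution for a paired test, one-sided testing needs n = 27 (power 82.5% at 28). Two-sided testing needs n = 34 (power 72.3% at 28). So 28 fits a one-sided test. The main results below are two-sided, with one-sided results alongside.

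**3. Model for the adjustment.** Let L and R be the within-person gamma-minus-control differences in learning and recall, each with SD 1, correlated r. Let m be the share of the effect that runs through learning. The documents give neither r nor m, so both are assumed and varied.

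- Mean of L = m x 0.5 / r
- R = (1-m) x 0.5 + r x L + sqrt(1-r²) x e, with e standard normal
- Total effect = (1-m) x 0.5 + r x (m x 0.5 / r) = 0.5
- Effect adjusted for L (the intercept) = (1-m) x 0.5

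The estimate therefore shrinks in proportion to m, whatever r is.

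**4. Power by simulation, n = 28, r = 0.7, two-sided 0.05**

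| m | Estimate without L | Estimate with L | Power without L | Power with L |
|---|---|---|---|---|
| 0 | 0.50 | 0.50 | about 72% | 94% |
| 10% | 0.50 | 0.45 | about 72% | 88% |
| 25% | 0.50 | 0.375 | about 72% | 74% |
| 50% | 0.50 | 0.25 | about 72% | 38% |
| 100% | 0.50 | 0 | about 72% | 5% |

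Two forces oppose each other. The residual SD falls to sqrt(1-0.49) = 0.714, which helps. The estimate falls to (1-m) x 0.5, which hurts. At r = 0.7 they roughly cancel near m = 25%.

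**5. Sensitivity to r.** At m = 50%, two-sided adjusted power is about 17% at r = 0.3, 26% at 0.5, 38% at 0.7 and 51% at 0.8. One-sided, with order in the model, unadjusted power is about 82%. Adjusted power at m = 50% is then 26%, 37% and 52% for r = 0.3, 0.5 and 0.7.

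**6. Next-day ratings.** The same algebra applies, with m read as the share running through sleep or next-day state. No separate figures were computed, because the documents give nothing from which to set that share or the correlation.

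**The case against.** The strongest reply is that the analysis plan does not prescribe this adjustment. Section 8.3 names order as the covariate and carries the same covariates over to the secondary outcomes. Section 8.1 only permits more. Table 1 reads partly as an inventory: it gives covariate uses to club membership, media consumption, handedness and other items that a model for 28 people could not carry together. This stands. A reader might infer that the Aim 2 ANCOVA will adjust for learning; the documents do not say so. They allow it and assign these variables that role, which is enough to need closing.

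A reader might also infer that all the listed covariates would erase an encoding effect. They would not. Next-day sleepiness, mood and sleep quality arise after encoding and do not block that route. They can only absorb an effect through sleep or next-day state. Aim 4 itself concerns EEG spindles and slow wave sleep, not self-rated sleep quality.

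Nor does adjustment always cost power. With little or no mediation through learning it raises power, as the first two rows of the power table show. Full mediation at r = 0.7 would need a learning effect of 0.5 / 0.7 = 0.71, larger than the recall effect the trial plans for.

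Footnote 4 to Table 1 mentions mediation analyses, and its marker may have been lost in the text extraction. As the text stands, no row carries that marker and the footnote also refers to medication adherence, so it cannot be relied on to restrict these rows.

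Listing a score as both outcome and covariate is not in itself an error; recall given learning is a fair retention question if labelled as such. Finally, section 2.2 says a memory effect is not needed to proceed to a full trial, and section 9 ties the sample size to feasibility. That limits the stakes but does not alter what the recall contrast should estimate.

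**Conclusion.** The point holds as a conditional one. Table 1 offers post-treatment variables as Aim 2 covariates, section 8.3 names only order, and section 8.1 leaves the door open. If the learning scores are used, the contrast becomes the part of the effect that bypasses encoding, (1-m) x 0.5 instead of 0.5. If the next-day ratings are used, any part acting through sleep or next-day state can be lost.

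The shrinkage of the estimate follows from the model for any m above zero. The effect on power depends on m and r: at r = 0.7 it runs from a gain (72% to 94%) with no mediation to a fall to 5% with full mediation. Because m cannot be known before the data, the covariate list should be fixed in advance. This should be corrected, though it does not show that the planned primary model is wrong as written in section 8.3.

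**What to change.** In Table 1 and section 8.3:

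- Remove the covariate role of RAVLT trials 1-7 and word-pair trials 1-4 at D1A/D1B, and of sleepiness, PANAS and sleep quality at D2A/D2B, for the Aim 2 recall contrasts.
- State that covariates for these contrasts are limited to order/period and values taken before stimulation starts. The D1A/D1B sleepiness, mood and sleep-quality ratings may stay, as period-specific covariates. Make the open clause in section 8.1 subject to this limit.
- Keep the learning scores as outcomes. Label any learning-adjusted or sleep-adjusted analysis as a secondary retention or mediation analysis.

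No visit, test or data item changes; the cost is wording. The real downside is losing the variance reduction from the learning score, which would raise power if little of the effect runs through learning.

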5.1. Numbers of Participants

5.1.1. Number to be screened: $N \leq 100$

5.1.2. Number to be enrolled: $N \leq 50$

The sample size is 28 participants in the final dataset, i.e. the participants who completed all the visits for the primary outcomes, i.e. Visits 1, 2, 3, 4, 5, 6, 7 (including the three nights with EEG). However, to ensure that 28 participants complete the experiment, we conservatively estimate to screen 100 participants and to enroll 50 participants as a ceiling for the sake of IRB approval. The motivation for the sample size of 28 participants is the following power analysis: power analysis: $dz = 0.5$, $1-\beta = 0.80$, $\alpha = 0.05$. Participants who drop-out or have missing data will be replaced.

Recruitment takes place in the general population.

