7.5. Early Discontinuations

Data to be Collected

If the study participation has to be terminated early by the investigators (due to safety concerns), or if a participant chooses to withdraw from the study, including the case of not showing up for scheduled visits on site (Visits 1, 2, 3, 5, 6), the data collected to date will not be included for the cognitive and sleep-EEG outcomes and the participant will be replaced. However, early discontinuation will be included in the data set for the feasibility outcomes as appropriate. Visits 4 and 7 are not mandatory for study completion.

Criteria for Intervention Discontinuation

An investigator may discontinue or withdraw a participant from the study for the following reasons:

- Any clinical adverse event (AE), intercurrent illness or other medical condition, or situation occurs such that continued participation in the study would not be in the best interest of the participant.

- The participant meets any exclusion criteria (either newly developed or not previously recognized) or a reason for immediate early termination of participation.

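### Section 5.1's completer set and missing-data replacement rule are not limited to the efficacy outcomes, so a full attender replaced for missing data may drop out of the feasibility denominators

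*Combined protocol and SAP*

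**What the plan says.** Section 5.1.2 defines the analysis sample by completion: "The sample size is 28 participants in the final dataset, i.e. the participants who completed all the visits for the primary outcomes". It lists Visits 1 to 7 and the three EEG nights, and then gives the replacement rule: "Participants who drop-out or have missing data will be replaced". Neither sentence exempts the feasibility aims.

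Feasibility is among the primary outcomes. Table 1 (section 4.3) has the row "Completed | Binary | D1A, D2A, D1B, D2B | Aim 1 | Primary outcome" and gives the same role to the first-night recording and to "EEG worn for ≥4h hours in 3/3 nights". Section 9 calls this a feasibility study with feasibility as its primary outcome. Table 1 also labels memory recall and spindles/slow-wave sleep as primary, and section 8.3 calls next-day recall primary.

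Section 7.5 is narrower than section 5.1. For people who withdraw, miss on-site visits or are ended by the investigators, "the data collected to date will not be included for the cognitive and sleep-EEG outcomes and the participant will be replaced". It continues that "early discontinuation will be included in the data set for the feasibility outcomes as appropriate".

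Section 8.3 gives a proportion of participants with a 95% confidence interval for Aims 1 and 3, and names no analysis set. Section 9 refers to the study sample without defining it. It uses 28 for people recruited, whereas section 5.1 uses 28 for people who complete.

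**The concern.** A feasibility proportion means something only if the people who could not do the procedure are in its denominator. Section 5.1 replaces people for missing data, and for Aims 1 and 3 the missing data can be the failure itself: no usable recording on a study night, or testing under stimulation not finished. If the section 5.1 set is used for those aims, such people leave both the count of failures and the denominator, and a successor takes their place.

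Section 2.2 says that the pilot prepares a full-scale trial by examining feasibility, acceptability and adherence, and that an effect on memory or sleep is not required for that step. The 80% verdicts therefore carry the main decision, and they should not depend on a denominator settled after the data are in.

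**Working it through.** **1. The plan's own figure.** The sample size of 28 is not the problem.
- Section 9 (null 50%, alternative 80%, alpha 0.05, 95% power): a one-sided exact binomial test at n = 28 rejects at 19 or more successes, with alpha 0.0436 and power 0.961. No n from 20 to 27 reaches 95%. A two-sided test needs 20 or more successes and has power 0.910. Sidedness is not stated.
- Section 5.1 (dz = 0.5, 80% power, alpha 0.05): a one-sided paired t-test needs 27 and has power 0.825 at 28. A two-sided test needs 34 and has power 0.723 at 28.

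**2. Who is placed, and who is not.**
- Withdrawn, not attending, or ended for safety: section 7.5 keeps them for feasibility.
- Ended for another listed reason: arguably also kept, because the section 7.5 criteria include "or a reason for immediate early termination of participation".
- Attends every on-site visit but is replaced for missing data: covered by section 5.1, not clearly by section 7.5, and not mentioned in section 8.3 or section 9.
- Short recording on night 2 or 3: section 5.1 does not say that its EEG nights must reach 4 hours. On that reading the person stays among the 28 and counts as an Aim 3b failure, so the gap concerns missing or unusable nights.

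**3. Effect on the verdict.** Let x be the completers (of 28) who meet the endpoint, and k the full attenders replaced because the endpoint's own data are missing.
- Section 5.1 applied to feasibility: x/28.
- Everyone kept: x/(28 + k).
- Aim 3b (synopsis criterion at least 80%) fails when x/(28 + k) < 0.80, that is, k > x/0.80 − 28.
- Aim 1 (criterion more than 80%) fails when k ≥ x/0.80 − 28.

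Aim 3b:

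| x | x/28 | x/0.80 − 28 | smallest failing k | rate with all kept |
|---|---|---|---|---|
| 28 | 100% | 7 | 8 | 28/36 = 77.8% |
| 26 | 92.9% | 4.5 | 5 | 26/33 = 78.8% |
| 25 | 89.3% | 3.25 | 4 | 25/32 = 78.1% |
| 24 | 85.7% | 2 | 3 | 24/31 = 77.4% |

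Exact (Clopper-Pearson) 95% intervals: 28/28, 87.7 to 100; 28/36, 60.8 to 89.9.

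Aim 1 with x = 28: k = 6 passes (28/34 = 82.4%) and k = 7 fails (28/35 = 80.0%, interval 63.1 to 91.6), because the criterion is strict.

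**4. With section 7.5 credited.** Discontinuations kept as failures use up part of the margin. As an illustration, take 28 successes, 4 discontinuations and 4 full attenders replaced for missing data. The rate is 28/32 = 87.5% if only the discontinuations are kept, and 28/36 = 77.8% if all are kept.

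**The case against.** The strongest reply is that section 5.1 is about efficacy. Its power statement is a paired effect size, and the replacement sentence follows directly. Visits 4 and 7, which it lists, are telephone calls for recall and adverse events and serve no feasibility endpoint. Section 7.5 removes discontinuers from the cognitive and sleep-EEG outcomes only. Section 9 asks whether at least 80% of the sample complete, which presupposes non-completers in it. Section 8.3 and the synopsis speak of participants, not completers.

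Much of this stands. It shows the probable intent and narrows the problem to full attenders replaced for missing data. It does not place those people. The EEG nights in section 5.1 serve Aim 3 as well as the sleep outcomes, Table 1 gives both the primary label, and no sentence settles the denominator.

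Three stronger readings are tempting, and the documents do not support them:
- *Feasibility is analysed on completers only and is 100% by construction.* No passage says so, section 7.5 says otherwise for discontinuations, and a completer with a short night can still fail Aim 3b.
- *The enrolment ceiling of 50 gives a realistic worst case.* That would need 50 − 28 = 22 replaced people who all failed the endpoint. Section 5.1 presents the ceiling as a conservative figure for ethics approval, and section 5.4 expects low drop-out.
- *Short first nights are removed and inflate Aim 3b.* This requires the termination entry in Table 1 to be in force and section 7.5, which arguably keeps such people, to be set aside.

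**Conclusion.** The point holds in a narrow form and should be fixed. Section 5.1 states a rule that, if applied to Aims 1 and 3, removes some of the failures that those aims count. Section 7.5 closes this for early discontinuations but not clearly for people replaced for missing data, and sections 8.3 and 9 do not close it.

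The size depends on k, for which the documents give no figure. The low drop-out expected in section 5.4 is argued from visit burden and does not address failed recordings. With every completer succeeding and no other failures, 8 such people are needed to change Aim 3b and 7 to change Aim 1. Fewer suffice when completers are already nearer 80% or when discontinuations are also counted. If the evident intent of section 7.5 is extended to these people, the bias disappears.

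Two contradictions touch the same definitions and need reconciling, although neither enters the figures above. Section 5.1 lists Visits 4 and 7 among those completed, while section 7.5 says "Visits 4 and 7 are not mandatory for study completion". Table 1 and section 7.1 treat under 4 hours on night 1 as ending participation or as an eligibility check, while the synopsis termination list, the exclusion list and the Visit 2 steps contain no such rule.

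**What to change.** - **Section 5.1:** state that the 28-completer set and the replacement rule apply only to the memory and sleep-EEG outcomes, in line with section 7.5.
- **Section 8.3:** state that everyone replaced, for any reason, stays in the feasibility denominators, with non-completion counted as failure. For Aim 3, use all eligible participants given the headband. For Aim 1, use all eligible participants who begin the Visit 2 stimulation procedures, including amplitude thresholding. Thresholding comes before stimulation, so a denominator starting at stimulation would miss people who stop there.
- **Reporting:** give exact 95% intervals and the number enrolled. Add a sensitivity analysis for endings unrelated to the headband or stimulation, such as alcohol use or a new diagnosis.
- **Section 9:** say which set its 28 refers to.
- **Reconcile** section 5.1 with section 7.5 on Visits 4 and 7, and the night-1 entries in Table 1 and section 7.1 with the synopsis, the exclusion list and the Visit 2 steps. Which rule applies is for the sponsor.

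The cost is protocol and SAP wording. No new data are needed, because section 7.6 already records reasons for drop-out and missing data. The downside is that the reported feasibility rates may be lower.
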